This document describes the statistical analysis plan (SAP) for the PIRATES-COV trial. The SAP was developed according to guidelines found in ICH E9. This SAP contains more technical and detailed elaboration of principal features of the analysis described in the protocol, and includes procedures for executing the statistical analysis of the primary and secondary variables. Planned ancillary studies will not be included in this SAP and will have their own separate SAP. Other unplanned exploratory analyses not identified in the SAP will be clearly identified in the reporting as well as any deviation in the analyses from this original SAP.

The SAP should be executed once the trial database lock (DBL) has been achieved. Analyses will be double-blinded for the randomization group. All the analyses will follow the Statistical Analysis Plan (SAP) described in this document. Analyses will be done under the responsibility of the trial statistician at the Data Coordinating Center (Applied Clinical Research Unit (URCA), CHU-Sainte-Justine, Montreal).

During the analysis processes, the study Principal Investigator, the Executive Committee and the Steering Committee will be kept blind to the randomization group until final disclosure of the study results.

5. Statistical analysis plan revisions

Any changes to the SAP will be logged in the following table:

Protocol version	Updated SAP version	Section number	Description of and reason for change	Date changed

6. Roles and responsibilities

Principal Investigator

[name] PhD, CRC-CHUS et Département de gynécologie/Obstétrique Faculté de médecine et des sciences de la santé (FMSS), Université de Sherbrooke (UdeS)

Research Co-presenters

[name], Centre de recherche sur le vieillissement du CIUSSS de l'Estrie-CHUS, UdeS

[name], CR-CHUS et Immunologie-Biologie cellulaire, FMSS, UdeS

Collaborators

[name], Médecine, FMSS, UdeS

[name], Sciences de la santé communautaire, FMSS, UdeS

[name], Immunologie-Biologie cellulaire, FMSS, UdeS

[name], Microbiologie et immunologie, Faculté de médecine, ULaval

[name], Gynécologie et obstétrique, Faculté de médecine, ULaval

[name], Gériatrie, FMSS, UdeS

[name], Sciences de la santé communautaire, FMSS, UdeS

[name], Biologie, Faculté des sciences, UdeS

[name], Médecine sociale et préventive, École de santé publique, UdeM

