Microbiota could partly explain the variations in flu vaccine responses between individuals or populations. Two meta-analyses have studied the effect of probiotics in the context of influenza vaccination. Lei et al. (9 RCTs, N=623) showed a significant improvement in antibody levels for the H1N1 strain (OR=1.83, 95% CI 1.19-2.82), the H3N2 strain (OR=2.85, 95% CI 1.59-5.10), and the B strain (OR=2.11, 95% CI 1.38-3.21). Yeh et al. found similar results with a significant increase in antibody levels (+20% A/H1N1, +19.5% A/H3N2, and +13.6% B). In 2019, an RCT showed an increase in immune response to the flu vaccine in an elderly population. These studies have limitations, often with small sample sizes and significant variability in: i) the probiotic (strain, dose, viability) and ii) mode of administration (e.g., duration). It has also been shown that antibiotics reduce the effects of vaccine boosters in people with low pre-existing antibodies concentrations.

8. Study Objectives

Primary objective:

Reduce the percentage of elderly individuals not presenting RBD antibodies, six months after the booster vaccine dose, through the intake of two strains of probiotics compared to placebo.

Secondary objectives (Obj S):

Obj S1: Compare between study groups the presence of RBD antibodies through a longitudinal analysis at three different time points (baseline, 3 months, and 6 months post-vaccination).

Obj S2: Compare between study groups the presence of anti-N antibodies through a longitudinal analysis at three different time points (baseline, 3 months, and 6 months post-vaccination).

Obj S3: Compare the proportion of the antigens or PCR confirmed cases of COVID-19 with symptoms and the proportion of COVID-19 asymptomatic cases between study groups.

Obj S4: Compare the evolution of antibodies and memory B cells, CD4+ T cells, and CD8+ T cells at baseline and 6 months post-vaccination (between study subgroup of participants).

Section 3: Trial Methods

9. Trial design

Inclusion Criteria:

- Men or women aged between 65 and 89 years
- having received 3 doses of an mRNA vaccine (Pfizer-BioNTech or Moderna), with the last dose being more than five months ago
- willing to receive a booster dose of the vaccine
- having access to a phone or the internet
- capable of providing informed consent
- residing in the province of Québec

Exclusion Criteria:

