- patients who had COVID-19 in the last 3 months (clinical and/or serological data retrospectively, subgroup of 100 participants only)
- patients already taking part in another randomized clinical study
- with possibly affected cognitive functions (a score < 9 is needed for inclusion according to the Functional Activities Questionnaire (FAQ))
- consuming probiotics on the day of inclusion
- with allergies (soy, lactose, yeast, maltodextrin)
- consuming antibiotics on the day of inclusion
- with a chronically weakened immune system (AIDS, etc.) or undergoing anti-cancer treatment (chemotherapy or radiotherapy)
- actively being treated for a gastrointestinal condition or disease (gastric ulcers, Crohn's disease, celiac disease, ulcerative colitis, etc.)
- Any other serious condition that, in the judgment of the study physician, would prevent safe participation in the study until the end
- Not speaking either French or English

All subjects in the study are asked to collect a dried blood sample at three different time periods (inclusion, 3 months and 6 months), and a stool sample at the time of inclusion. A subsample of

subjects (n = 100) was selected to undergo additional blood tests at two different time periods (inclusion and 6 months); this subsample is used for the secondary analysis S4.

10. Randomization

Randomization is carried out with a 1:1 ratio, probiotics (intervention) versus placebo after inclusion. Prior to the start of the study, the randomization list will be generated by the statistician considering age and gender stratification. Age stratification will be done in 2 strata: 65-79 years old and 80-89 years old.

Randomization will be done via the REDCap application. The statistician will create different randomization tables according to gender (female/male) and age strata. These tables will then be imported into REDCap for automatic randomization based on the age and gender information of each participant.

During the course of the trial and until the database is locked, study personnel at the site (principal investigator and research team) and at the Sponsor (research specialists and laboratory manager) will not be informed of the group allocation. Based on a blinded randomization method (according to the algorithm built into the REDCap platform), participants will be assigned to one of the 2 groups. The CHUS pharmacy will prepare the products according to the allocation on REDCap.

11. Level of statistical significance

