The primary outcome measure is a measure of RBD antibodies. We consider the dichotomous value (detectable or undetectable) for the level of statistical significance. We used an expected proportion of 30% of elderly individuals not presenting RBD antibodies in the placebo group at 6 months. Expecting that the intervention is over-the-counter and inexpensive, we calculated the sample size to detect a relative difference of 33%, with a two-sided alpha of 5% and a power of 80%; 584 participants are required. With a 15% attrition rate at 6 months, the total sample size is 688 patients.

Final analyses will begin in 2025 after database lock.

Unless otherwise specified, the alpha will be set at 0.05 for statistical significance.

12. Adverse events reporting

Taking probiotics has very few undesirable side effects, unless taken in doses higher than the recommended dosage (bloating, intestinal irritation, constipation). Side effects for probiotics (product adherence, medication intake, adverse effects) will be collected once every 2 weeks for 33 days. For the booster vaccine dose, all adverse events, such as local reactions (pain at the injection site or arm, local erythema, lymphadenopathy) and systemic reactions (fever, fatigue, headaches, joint pain, digestive issues, flu-like symptoms...) will be recorded once a week for 2 weeks. If a participant reports symptoms related to an infection, we will ask them to realize a COVID-19 test. If the participant is unable to get tested, we will provide them with a box of rapid tests for self-testing. If a participant needs to be hospitalized, data related to the hospitalization

will be collected. This process will be carried out with the utmost respect for the healthcare teams' work, aiming not to add extra workload. Various data collection methods are possible:

- From the medical records after the end of hospitalization;
- By contacting the patient after discharge by phone or email;
- We will ask the participant at the beginning of the study to inform us of their place of care if they leave their home;
- By contacting the designated reference person identified at the beginning of the study.

The monitoring committee will ensure the safety of the participants and will be notified of any serious adverse events (within 48 hours) and non-serious adverse events (one monthly report).

13. Definition of adherence and how adherence will be presented

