Adherence will be estimated via self-reported adherence in the logbooks pre-vaccination and post-vaccination completed online or on paper (according to the preference of the participant). If at least 80% of the doses prescribed was taken both pre and post vaccination (i.e. 12 pills out of 15 for both periods), and if no more than 120% of the total dose prescribed was taken (i.e. no more than 36 pills), we consider that the participant adhered to the protocol.

14. Lost to follow-ups and withdraws

We conservatively anticipated that 15% of participants would be lost to follow-up at 6 months. The observed number of lost subjects was lower, as only 9.8% of subjects were lost at some point during the study.

[figure not shown]
15. Definition of analysis populations e.g. Intention-to-treat, per-protocol

Intent to treat analyses will include all participant randomized to either control or intervention arm including participants lost to follow up.

Per-protocol analyses will include all participant randomized to either control or intervention arm, excluding participants lost to follow up, those with less than 80% adherence for each period (or with more than 120% adherence in total) to the assigned intervention, subjects with 5 months or less between the their last vaccine dose and their scheduled booster dose, subjects who did not get the booster shot as planned, subjects taking probiotic supplements at inclusion, during product intake or more than one week in continuous during the follow up phase subjects with other previous vaccines than Pfizer-BioNTech or Moderna, and subjects taking antibiotics at inclusion or during product intake(antibiotics taken less than 2 hours before the treatment probiotic or placebo).

16. CONSORT Diagram

Per recommendations in the CONSORT guidelines, the statistician will generate a flow chart indicating the number of individuals screened and enrolled, the reasons for ineligibility, the number of individuals randomized, and the number of participants in each group who provided blood samples at each stage of the study.

17. Descriptive analyses and positivity checks

Distribution of sociodemographic and clinical variables measured at inclusion will be described for each group. The proportion of missing data will be described for each variable. Continuous variables will be presented as means and standard deviations or geometric means and 95% confidence intervals (CIs). Categorical variables will be presented as N (%).

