RBD antibodies: i) can powerfully block the binding between SARS-CoV-2 and its ACE2 receptor, and ii) are a correlate of antibodies and vaccine efficacy. The RBD antibody level will be determined by a validated ELISA test (95% sensitivity and 100% specificity). The primary outcome measure is a dichotomous measure of RBD antibodies (detectable or undetectable). The positivity threshold was defined based on the mean optical density (colorimetric reaction on blotting paper) of negative sera +3 SD. Possibly, a quantitative variable will be available.

Secondary outcomes

The Anti-N antibodies will be determined by the same procedure than for the dichotomous RBD antibody level (90% sensitivity and 95% specificity).

For the comparison of asymptomatic versus symptomatic COVID-19 cases, a subject will be classified as asymptomatic if the anti-N test confirms that the subject had COVID-19, but the subject never reported a positive COVID-19 test during the time period.

For the Ac (OS 4): we will perform a pseudotyped viral neutralization test. The S protein expressed by the vesicular stomatitis virus and HEK293 cells overexpressing ACE2 will be used. Memory B, CD4+ T, and CD8+ T lymphocytes (OS 4) will be studied by flow cytometry. B cells will be identified with appropriate markers and the S protein coupled with a fluorochrome. Memory CD4+ and CD8+ T cells will be identified following activation by the S protein with the appropriate markers.

21. Descriptives analyses of outcome measures

Detectability of Ac RBD will be described and compared between groups using chi-squared or fishers exact tests as appropriate. If quantitative RBD measures are available will be compared by intervention arm using t-test or rank sum testing as appropriate based on the distributions.

Distribution of log of score measures will be calculated for each of: Ac-n and lymphocytes B, T CD4+ et T CD8+ at inclusion and 6 months post vaccine. The distributions will be generated overall and comparatively by intervention arm using t-test or rank sum testing as appropriate based on the distributions.

22. Stratifying variables

The analysis will follow the randomization strategy. Gender and age were used as stratifying variables. We will use the same categories in the analysis.

23. Primary outcome analyses

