The primary analysis on the dichotomous criterion (Ac RBD) at three time points (baseline, 3 months, and 6 months post-vaccination) will use a GEE logistic regression model with a logistic link function for longitudinal binary data. This model will also include the stratification variables used for randomization (age group and sex). The other variables included in the model are the group (placebo vs. probiotic) and time (baseline, 3 months, and 6 months post-vaccination). The main parameter of interest in this model will be the interaction between the group and time.

Logistic regressions will also be performed for fixed time strata (3 months and 6 months) to assess the effect of the group at specific time points.

If Ac RBD as a quantitative variable is available, a GEE regression model with appropriate link function for continuous outcome will be used. Generalized linear models will be used to assess the effect of the group at specific time points (3 months and 6 months).

If there are differences in censoring by group, an additional GEE model will be used with inverse probability of censoring weights (IPCW) to assess the bias potentially induced by attrition during follow-up to 6 months. This method first estimates the probability of dropout to construct IPCWs, and then fits the GEE model with these IPCWs.

24. Secondary outcome analyses

The analysis for N antibodies at three time points between study groups will follow the approach described for RBD antibodies as a dichotomous variable.

For COVID-19 confirmed cases, a chi-squared test of independence will be used to compare the proportion of symptomatic and asymptomatic participants between the study groups. Cox proportional hazard models will be used to compare the risk of a COVID-19 outcome between the study groups, measured at six different time points.

The Ac criteria and B, CD4+ T, and CD8+ T lymphocytes are measured at baseline and 6 months post-vaccination. These criteria will be analyzed on their original log-transformed measurement scales (continuous variables). ANCOVA will be used to compare the groups at 6 months post-vaccination using the baseline measurement as a covariate. The CD4 or CD4/CD8 ratio with Ac-n (log-transformed) will be estimated using Spearman's correlation with a 95% confidence interval.

25. Adverse and Serious adverse events

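### Section 23 lists no covariates for the supplementary 3- and 6-month RBD models; adjusting them for baseline RBD is a cheap, optional gain in precision

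*SAP*

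**What the plan says.** - **Objective (section 8).** The primary aim is a 6-month contrast: "Reduce the percentage of elderly individuals not presenting RBD antibodies, six months after the booster vaccine dose". Section 11 sizes the trial on the same contrast: 30% undetectable on placebo, a 33% relative reduction, 584 evaluable participants. It adds: "With a 15% attrition rate at 6 months, the total sample size is 688 patients".
- **Primary model (section 23).** A logistic GEE over baseline, 3 and 6 months, with age group and sex as covariates and group-by-time as the main parameter. Baseline RBD is one of the three repeated responses.
- **Models at single visits (section 23).** "Logistic regressions will also be performed for fixed time strata (3 months and 6 months) to assess the effect of the group". If RBD is available as a quantity, generalized linear models do the same job. Section 20 leaves that open: "Possibly, a quantitative variable will be available". No covariates are listed for either.
- **General rule (section 22).** The randomisation strata, gender and age, are carried into the analysis. No other covariate is named.
- **Other outcomes (section 24).** The S4 antibody and cell measures are compared at 6 months by ANCOVA with the baseline value as covariate. Anti-N follows the approach set out for dichotomous RBD.
- **Availability of baseline RBD (sections 9 and 10).** "All subjects in the study are asked to collect a dried blood sample at three different time periods (inclusion, 3 months and 6 months" describes the sampling, and "Randomization is carried out with a 1:1 ratio, probiotics (intervention) versus placebo after inclusion" the order of events. By plan, baseline RBD is therefore a pre-treatment value.

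**The concern.** Of all the planned models, the 6-month logistic regression estimates the contrast of the primary objective and the sample size most directly. A pre-treatment measurement of the same variable is usually among the stronger candidate covariates, and here it needs no new data. Leaving it out gives up some precision and some protection against chance imbalance at baseline. Leaving the covariates unlisted also leaves the choice open until the data are in hand.

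The size of the loss depends on how well RBD at inclusion predicts RBD at 6 months. A booster falls between the two samples, so the link may be weak.

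**Working it through.** **1. The plan's own figures.** With 0.30 vs 0.20, two-sided 5%, 80% power and 1:1 allocation, the arcsine formula has h = 2·asin(√0.30) − 2·asin(√0.20) = 0.232. Then n = 2·((1.960 + 0.842)/0.232)² = 291.7, so 292 per arm and 584 in total, as stated. The pooled formula gives 588. For attrition, 584/0.85 = 687.1, or 688 in two equal arms. Closed-form power is 79.8% at 292 per arm. Section 14 reports 9.8% lost; if 688 were randomised, 688 × 0.902/2 = 310 per arm and power is 82.2%.

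**2. Assumed inputs.** The SAP gives neither the share undetectable at baseline nor the correlation. Baseline undetectable is taken as 2-30% and the correlation of the underlying (latent, bivariate-normal) antibody values as 0.3-0.7.

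**3. Latent versus binary correlation.** Dichotomising weakens correlation. With 25% undetectable at 6 months (midway between 30% and 20%) and 5-30% undetectable at baseline, the correlation of the yes/no results is:

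| Latent | Binary |
|---|---|
| 0.3 | about 0.12-0.18 |
| 0.5 | about 0.22-0.31 |
| 0.7 | about 0.32-0.47 |

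**4. Closed-form check.** Adjustment multiplies the variance by about 1 − r², with r the binary correlation, so 292 per arm acts like 292/(1 − r²).
- r = 0.18: 292/0.968 = 302, power 81.1% (+1.3 points).
- r = 0.31: 292/0.904 = 323, power 83.7% (+3.9).
- r = 0.47: 292/0.779 = 375, power 88.7% (+8.9).

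**5. Simulation.** 3,000 trials per cell, 292 per arm, age group and sex in both models, Wald p < 0.05. The strata inputs are also assumed: 20% aged 80-89, 50% male, latent shifts of 0.30 and 0.15 SD. Power (%) without/with baseline RBD; the Monte Carlo SE of each figure is about 0.7 points, and both models are fitted to the same data:

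| Undetectable at baseline | latent 0.3 | latent 0.5 | latent 0.7 |
|---|---|---|---|
| 2% | 81.2/81.4 | 80.3/81.7 | 81.3/82.5 |
| 5% | 81.6/82.3 | 79.9/82.0 | 80.6/84.7 |
| 15% | 80.8/81.3 | 80.5/84.3 | 80.4/88.4 |
| 30% | 80.8/81.8 | 80.1/84.1 | 78.6/87.9 |

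Simpler runs without strata (2,000 trials per cell, 5% and 30% undetectable) gave gains of about 0.1-1.4, 1.5-2.9 and 4.5-8.0 points. At latent 0.1 the change was −0.1 to +0.4. The largest gain in the table, 9.3, sits in the cell with the lowest unadjusted power, so it is probably a little high; step 4 gives 8.9.

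**6. Chance imbalance.** A 1-SD chance imbalance in baseline RBD moves the unadjusted 6-month difference by 0.3-0.7, 0.6-1.2 and 0.7-1.8 percentage points at latent 0.3, 0.5 and 0.7, against a 10-point target.

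**7. What the covariate brings with it.**
- *Non-convergence.* At 2% undetectable, the adjusted model failed to converge in about 0.6%, 4% and 35% of trials at latent 0.3, 0.5 and 0.7. The model without baseline RBD was used there.
- *Missing baselines.* With 10% missing at random and 310 per arm (5% and 30% undetectable), dropping those participants changed power by −3.6 to −2.5 points at latent 0.3 and by −2.3 to +0.1 at 0.5. A missing-indicator gave +0.6 to +0.9 and +1.8 to +3.3.
- *Type I error.* In null simulations it was 3.9-5.6% with adjustment and 4.4-5.8% with the missing-indicator (SE about 0.4).

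**8. Quantitative RBD.** The factor 1 − r² applies directly: variance falls by 9%, 25% and 49% at r = 0.3, 0.5 and 0.7.

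**The case against.** The strongest case against raising this is that nothing is wrong. Randomisation makes the unadjusted comparison valid, no figure in the SAP changes, and the primary GEE already uses baseline RBD as a response. The models in question are supportive, the gain rests on assumed inputs, and adjustment brings a missing-baseline rule and a convergence fallback that the present plan does not need. Most of this stands, and it is why the point is optional. It does not remove the point, because the 6-month model estimates the contrast that sized the trial and the covariate is already requested from everyone.

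Four stronger readings are tempting, and the SAP does not support them.
- **That it excludes baseline RBD.** It is silent. Adjustment for age group and sex only is an inference, though a natural one, since section 24 spells out baseline adjustment where it is meant.
- **That the planned comparison is biased.** It is not; only precision is at issue.
- **That the S4 ANCOVA makes the plan inconsistent.** Those measures are continuous, taken at two times in 100 participants and have no longitudinal model. RBD is dichotomous, measured three times and has one. Different models are defensible.
- **That a correlation of 0.5 brings about 10 points of power.** That holds for a binary correlation of 0.5, which is slightly beyond latent 0.7 with 30% undetectable at baseline. At latent 0.5 the gain is 1.5-4 points.

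One practical objection also stands: anti-N inherits the RBD approach, so a change to section 23 alone would leave it unclear which baseline the anti-N models use.

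**Conclusion.** This is a low-priority improvement, not an error. At 292 per arm with 5-30% undetectable at baseline, baseline adjustment adds about 0-1.5 power points at latent correlation 0.3, 1.5-4 at 0.5 and 4-9 at 0.7. Gains above 5 points appeared only at latent 0.7 with at least 15% undetectable at baseline. If nearly everyone is detectable at inclusion, or the booster breaks the link between the two samples, the gain is near zero. At 310 per arm the pattern is similar. Confidence is medium: the covariate list is inferred from silence, and both inputs that drive the size are assumptions.

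**What to change.** 1. In section 23, state that the 3- and 6-month models adjust for age group, sex and baseline RBD status, or log baseline level if quantitative RBD is available.
2. State one rule for missing baselines: keep these participants with a missing-indicator.
3. State one fallback: use the age-and-sex model if the adjusted model does not converge.
4. Report a standardised 6-month risk difference beside the conditional odds ratio.
5. In section 24, state that the anti-N models at single visits adjust for baseline anti-N, not baseline RBD.
6. Record the change before unblinding in the section 5 table, which exists for this: "Any changes to the SAP will be logged in the following table".

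The GEE, the descriptive comparisons in section 21 and the sample size stay as they are. The cost is a few sentences in sections 23 and 24 and one log entry, with no new data. The downsides are that the odds ratio becomes conditional on baseline RBD, and that the missing-baseline rule and the fallback are needed only because the covariate is added.

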The probability of intervention conditional on baseline variables will be calculated for all observations to confirm the effectiveness of randomization and to verify the balance of baseline factors in each intervention arm. Overall probability will be graphed to confirm that there are no violations of positivity. Should there be positivity violations, the statistician will investigate and characterize participants who have a less than 5% or greater than 95% probability of intervention. The statistician will then notify the investigators and discuss whether a restriction of the analysis is necessary.

To assess the quality of participant blinding, participants assessment of their arm will be compared against the true randomization status.

A table describing the demographic and clinical characteristics at baseline randomization will be generated, however statistical testing will not be done comparing individual variables between groups.

Participation in follow-up assessments and completeness of outcome data will be calculated and compared for each time point by study arm. A sensitivity analysis on loss to follow-ups will be performed using weights or extreme case scenarios.

18. Intention to treat

For the primary analyses, we will follow an intention to treat model. All participants will be assigned intervention status based on their randomized assignment. We will use an inverse probability of censoring for missing outcome data. Participants lost to follow-up will be censored.

19. Adherence per protocol analysis

Per-protocol analyses will include all participant randomized to either control or intervention arm, excluding participants lost to follow up or those non-adherent to the assigned intervention. Adherence will be estimated via self-reported adherence in the logbooks pre-vaccination and post-vaccination completed online or on paper (according to the preference of the participant). If at least 80% of the doses prescribed was taken both pre and post vaccination (i.e. 12 pills out of 15 for both periods), and if no more than 120% of the total dose prescribed was taken (i.e. no more than 36 pills), we consider that the participant adhered to the protocol.

20. Outcome definitions

Primary outcome

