Adverse events (AE), including serious adverse events (SAE), will be monitored and tracked using a logbook or monthly form asking participant if they had COVID-19 in the last month or any other adverse event self-reported at another moment. They will be coded according to MedRA standards and will be summarized per intervention group.

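### As worded, the S3 chi-squared test most naturally compares the symptomatic/asymptomatic split among infected participants only, which is not protected by randomisation and is not what objective S3 names

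*SAP*

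**What the plan says.** Three places in the SAP describe this comparison.

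- **Section 8, objective S3** compares between arms the proportion of "the antigens or PCR confirmed cases of COVID-19 with symptoms and the proportion of COVID-19 asymptomatic cases between study groups". It names two proportions and no denominator.
- **Section 20** opens the outcome definition with "For the comparison of asymptomatic versus symptomatic COVID-19 cases". A participant is asymptomatic if anti-N shows past infection "but the subject never reported a positive COVID-19 test during the time period". The stated anti-N accuracy is "90% sensitivity and 95% specificity".
- **Section 24** gives the test: "For COVID-19 confirmed cases, a chi-squared test of independence will be used to compare the proportion of symptomatic and asymptomatic participants", between the study groups. The same paragraph adds Cox models to "compare the risk of a COVID-19 outcome between the study groups, measured at six different time points". The preceding paragraph plans a longitudinal by-arm analysis of anti-N.

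On analysis sets, section 15 defines an intention-to-treat population of everyone randomised, but section 18 applies it narrowly: "For the primary analyses, we will follow an intention to treat model". Nothing says which set the S3 test uses.

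**The concern.** Infection happens after randomisation and may itself be affected by the probiotic. The infected participants in the two arms are then not comparable groups, and a difference in their symptom mix cannot be read as an effect of treatment. A within-case test also does not deliver what S3 names. It tests one ratio (symptomatic to asymptomatic), not the two proportions per arm. The ratio can stay still while both risks fall, and it can move while symptomatic risk is the same in both arms.

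There is also a gap in the classes. A participant with a positive antigen or PCR test but no symptoms is not a symptomatic case under S3, and is not asymptomatic under section 20, which requires that no positive test was reported.

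**Working it through.** **Reading the text.** Sections 20 and 24 both introduce the comparison as one of cases, and a chi-squared test of symptomatic/asymptomatic by arm is then naturally a 2×2 table of infected participants. S3 points the other way: among the infected the two proportions would be complements (apart from the unclassified group), so naming both makes more sense over each whole arm. No passage settles it.

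**Inputs.** The SAP states no figure for S3, so there is none to reproduce. From the SAP: 688 planned (section 11), 1:1 allocation (section 10), 9.8% lost (section 14), two-sided alpha 5% (section 11), anti-N accuracy 90%/95% (section 20). Participants with outcomes per arm: 688 × (1 − 0.098) / 2 = 310. Assumed: placebo risks of 20% symptomatic (s) and 10% asymptomatic (a), with a range of 10/5% to 30/15%, and a relative effect of 40%.

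**Formulas.**
- Symptomatic share among cases = s / (s + a).
- Two-proportion power = Φ[(|p₁ − p₂| − 1.96 × SE₀) / SE₁] plus the opposite tail, where SE₀ uses the pooled proportion and SE₁ the separate ones.
- Three-level table: noncentral chi-squared, 2 df.

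**Scenario 1, only asymptomatic infection cut by 40% (20/10% to 20/6%).** Cases: 310 × 0.30 = 93 and 310 × 0.26 = 80.6. Symptomatic share: 0.20/0.30 = 67% versus 0.20/0.26 = 77%. Symptomatic risk is 20% in both arms.

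**Scenario 2, both cut by 40% (20/10% to 12/6%).** Cases: 93 and 310 × 0.18 = 55.8. Share: 0.20/0.30 = 0.12/0.18 = 67% in both arms. For symptomatic risk over all participants, the difference is 0.08, the pooled proportion 0.16, SE₀ = √(0.16 × 0.84 × 2/310) = 0.0294 and SE₁ = √((0.20 × 0.80 + 0.12 × 0.88)/310) = 0.0293. Power = Φ[(0.08 − 1.96 × 0.0294)/0.0293] = 78%.

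**Scenario 3, infections only shift from symptomatic to asymptomatic (20/10% to 12/18%).** Share: 67% versus 0.12/0.30 = 40%.

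Probability of rejection, perfect classification, 310 per arm:

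| Scenario | Case-only | Symptomatic, all | Asymptomatic, all | Three-level, all |
|---|---|---|---|---|
| 1: 20/10% to 20/6% | 32% | 5% | 45% | 36% |
| 2: 20/10% to 12/6% | 5% | 78% | 45% | 89% |
| 2 at 10/5% to 6/3% | 5% | 45% | 25% | 53% |
| 2 at 30/15% to 18/9% | 5% | 94% | 63% | 99% |
| 3: 20/10% to 12/18% | 96% | 78% | 82% | 91% |

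**Effect of anti-N error.** Applying the section 20 accuracy to one anti-N reading in participants without a reported positive test, observed asymptomatic = 0.90a + 0.05(1 − s − a). In scenario 2 this gives 0.090 + 0.035 = 12.5% on placebo and 0.054 + 0.041 = 9.5% on probiotic. The observed shares become 20/32.5 = 62% and 12/21.5 = 56%, although the true share is 67% in both arms. Rejection rates: case-only about 11–12%, symptomatic 78%, asymptomatic 22%, three-level 82%. Part of any case-only signal here is a false change in mix.

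**The case against.** Four points deserve weight.

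1. **The opening phrase in section 24 may be only a topic label.** Other paragraphs there also begin by naming their outcome, and the Cox model in the same paragraph would make no sense if restricted to cases. If confirmed means antigen- or PCR-confirmed, as in S3, a literal restriction would leave the section 20 asymptomatic class empty. This stands: a reader might infer that the SAP explicitly limits the test to infected participants, and it does not. What remains is an ambiguity whose most natural reading is the unprotected one.

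2. **Other analyses compare arms without restriction to cases.** This also stands in part. One might infer that the whole COVID-19 comparison has lost randomisation, but the Cox and anti-N analyses are not limited to cases and partly cover infection overall. Neither is stated to separate symptomatic from asymptomatic infection. The six time points, with the "monthly form asking participant if they had COVID-19 in the last month" in section 25, suggest that the Cox outcome is reported COVID-19, but the SAP does not say so.

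3. **The 5% is not a failure of power.** Correct. In scenario 2 the symptom mix is unchanged, so the case-only null is true and 5% is the type I error. Scenario 3 shows the case-only test can be the most powerful. A claim that it is generally weaker is not supported.

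4. **Positive tests without symptoms may be few.** Section 12 asks participants with symptoms to test, so testing is largely symptom-prompted. The class is probably small, but its size is not known, and it still needs a rule.

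**Conclusion.** The concern holds as a matter of wording and of the question answered. Sections 20 and 24 most naturally describe a comparison within a post-randomisation subset, while S3 fits a whole-group denominator. Followed as most naturally read, the test could show a symptomatic share of 67% versus 77% with equal symptomatic risk, so that preventing asymptomatic infection looks like harm. It would also not report the two proportions in S3.

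All of the sizes rest on assumed infection rates and a 40% effect, on 688 as the number randomised, and on equal losses in the two arms. The weight is minor to moderate: one secondary objective is affected and the primary outcome is not.

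**What to change.** Reconcile sections 8, 20 and 24, and state in section 24:

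- **Denominator.** Compare by arm, over participants as randomised, (i) the proportion with symptomatic antigen- or PCR-confirmed infection and (ii) the proportion with asymptomatic infection; or use one three-level table (none, asymptomatic, symptomatic) by arm.
- **Missing anti-N.** Do not count participants without a follow-up anti-N result as uninfected by default. Either use the censoring weights named in section 18 or restrict to those with outcome data, and say which.
- **Baseline anti-N.** Base new asymptomatic infection on the change from the baseline result that objective S2 already uses.
- **Classes.** Assign a positive test without symptoms to one class.
- **Split among cases.** If kept, label it supportive and not protected by randomisation.

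The cost is SAP text and slightly more analysis work, with no new data. The asymptomatic proportion will have low power given the stated anti-N accuracy: about 22% in the scenario with both risks cut by 40%. That figure uses a single anti-N reading and would differ under a change-from-baseline rule.
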